4.4 WITHDRAWAL CRITERIA

Withdrawal procedure occurs if patients choose to exit the study or if they loose capacity. The clinical details up till the point of withdrawal of the patient from the study will remain on file.

5. ADVERSE EVENTS

5.1 DEFINITIONS

Adverse Event (AE): any untoward medical occurrence in a patient or clinical study subject.

Serious Adverse Event (SAE): any untoward and unexpected medical occurrence or effect that:

- **Results in death**
- **Is life-threatening** – *refers to an event in which the subject was at risk of death at the time of the event; it does not refer to an event which hypothetically might have caused death if it were more severe*
- **Requires hospitalisation, or prolongation of existing inpatients' hospitalisation**
- **Results in persistent or significant disability or incapacity**
- **Is a congenital anomaly or birth defect**

Medical judgement should be exercised in deciding whether an AE is serious in other situations. Important AEs that are not immediately life-threatening or do not result in death or hospitalisation but may jeopardise the subject or may require intervention to prevent one of the other outcomes listed in the definition above, should also be considered serious.

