5.3 REPORTING PROCEDURES

All adverse events should be reported. Depending on the nature of the event the reporting procedures below should be followed. Any questions concerning adverse event reporting should be directed to the Chief Investigator in the first instance.

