5.3.1 Non serious AEs

All such events, whether expected or not, should be recorded.

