5.3.2 Serious AEs

An SAE form should be completed and faxed to the Chief Investigator within 24 hours. However, relapse and death due to endometrial cancer and hospitalisations for elective treatment of a pre-existing condition do not need reporting as SAEs.

All SAEs should be reported to the JCRO at Imperial where in the opinion of the Chief Investigator, the event was:

- 'related', ie resulted from the administration of any of the research procedures; and
- 'unexpected', ie an event that is not listed in the protocol as an expected occurrence

Reports of related and unexpected SAEs should be submitted within 15 days of the Chief Investigator becoming aware of the event, using the NRES SAE form for non-IMP studies. The Chief Investigator must also notify the Sponsor of all SAEs.

Local investigators should report any SAEs as required by their Local Research Ethics Committee, Sponsor and/or Research & Development Office.

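### The SAE definition in 5.1 includes unexpectedness, which conflicts with 5.3.2 and lets a serious event judged expected miss the 24-hour form and Sponsor notification

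*Combined protocol and SAP*

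**What the plan says.** Section 5.1 gives two definitions. An adverse event (AE) is "any untoward medical occurrence in a patient or clinical study subject". An SAE is "any untoward and unexpected medical occurrence or effect that" has one of five outcomes: death, threat to life, new or prolonged hospitalisation, lasting or significant disability or incapacity, or congenital anomaly. A closing clause widens seriousness beyond those outcomes: "Medical judgement should be exercised in deciding whether an AE is serious in other situations".

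The reporting rules follow:

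- Section 5.3 sets the general duty: "All adverse events should be reported".
- Section 5.3.1, headed for non-serious AEs, says: "All such events, whether expected or not, should be recorded".
- Section 5.3.2 covers SAEs. First, "An SAE form should be completed and faxed to the Chief Investigator within 24 hours". Relapse or death from endometrial cancer and elective admissions for existing conditions are exempt. The Chief Investigator then decides which SAEs are both related and unexpected, and those go to the JCRO within 15 days. Unexpected is explained there as "an event that is not listed in the protocol as an expected occurrence". Separately, "The Chief Investigator must also notify the Sponsor of all SAEs".

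**The concern.** Seriousness and expectedness are different properties of an event. Seriousness describes the outcome; expectedness describes whether it was foreseen. The protocol's own reporting scheme uses them in sequence: seriousness starts the 24-hour report, and expectedness, together with relatedness, decides on onward reporting to the JCRO. Section 5.1 merges the two at the first step.

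At stake is who sees a serious event and when. The 24-hour form and the Sponsor notice have no expectedness filter of their own, so both inherit the one in 5.1. Whoever first classifies the event would settle expectedness before the Chief Investigator is told, although 5.3.2 gives that judgement to the Chief Investigator. If assessors differ in what they regard as expected, SAE counts will differ with them.

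**Working it through.** No arithmetic applies. The check is to set the rules side by side and follow one event through them.

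**Conditions at each step, as written**

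| Step | Section | Conditions |
|---|---|---|
| AE | 5.1 | untoward |
| SAE | 5.1 | untoward, unexpected, and one of the five outcomes |
| General report | 5.3 | any AE |
| Record | 5.3.1 | non-serious AE, expected or not |
| 24-hour form to Chief Investigator | 5.3.2 | SAE, not exempt |
| JCRO report within 15 days | 5.3.2 | SAE, related, unexpected |
| Sponsor notice | 5.3.2 | SAE |

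**Trace of a hospitalisation judged expected and not covered by an exemption**

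1. It is an AE, because that definition does not mention expectedness.
2. It is not an SAE under the literal wording of 5.1.
3. The 24-hour form is not triggered.
4. The Sponsor notice is not triggered.
5. If it also counts as expected under 5.3.2, the JCRO report would be ruled out by that section's own criterion, whatever 5.1 said.
6. The general duty in 5.3 still applies.
7. Section 5.3.1 applies if every AE that is not an SAE is treated as non-serious; the event is then recorded. If non-serious has its ordinary meaning, the event fits neither 5.3.1 nor 5.3.2, and only the general duty is left.

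**Redundancy.** Write S for one of the five outcomes, U for unexpected and R for related. Under 5.1, SAE = S and U. The JCRO set in 5.3.2 is SAE and R and U = (S and U) and R and U = S and U and R. The second U does nothing if the word has one meaning throughout. With U removed from 5.1, SAE = S, and the JCRO set is again S and R and U. The second test now does work, the JCRO set is unchanged, and the only events added to the 24-hour and Sponsor steps are those that are serious but expected.

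**Which test of expectedness applies in 5.1?** The section does not say. There are three possibilities:

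- *The 5.3.2 test, with no list.* No expected events are listed in the protocol text. Nothing is then expected, and the words in 5.1 exclude nothing.
- *The 5.3.2 test, with a list added or held elsewhere.* Every listed event with a serious outcome is then excluded from SAE status.
- *The assessor's clinical judgement.* Exclusion then depends on who classifies the event.

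On the first reading the words have no effect; on the other two they remove serious events from prompt reporting. The text does not choose among them.

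**The medical-judgement clause.** It carries no expectedness condition, but it is written for situations other than the listed outcomes, so it does not clearly bring an expected hospitalisation back. Read literally, a foreseeable event that merely might have led to hospital admission can be serious, while a foreseeable admission is not an SAE.

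**The case against.** Several points on the other side are sound.

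- **Such events are not lost altogether.** A reader might infer that a foreseeable death or hospitalisation falls out of every reporting route. The documents do not support that. Section 5.3 requires all AEs to be reported, 5.3.1 may well capture the event, and questions go to the Chief Investigator. The missing JCRO report follows from the criterion in 5.3.2 itself, at least where expected means the same in both sections.
- **A site is not compelled to exclude the event.** By the only meaning the protocol gives to unexpected, and with no list, every event is unexpected. This stands as far as it goes, but 5.1 does not adopt that meaning. The result is ambiguity, neither a forced exclusion nor a safe reading.
- **The exemptions in 5.3.2 are weak evidence of conflict.** They might seem needless if foreseeable events were never SAEs. But these women have only suspected cancer, so a death from endometrial cancer could be unexpected, and the exemption still has a use. The conflict rests on the repeated expectedness test, not on the exemptions.
- **Little depends on it here.** The study is observational, built on a 5-minute questionnaire, and the biopsy is done for clinical indications. Section 3 names one Trust as the setting, and section 7 plans no safety analysis. This limits the size of the problem. It does not make 5.1 and 5.3.2 agree, and 5.3.2 and 8.1 do provide for local investigators and participating Trusts.

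A reader might also suppose that serious but foreseeable events are the commonest kind in this study. The documents give no rates, so nothing supports that.

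**Conclusion.** The point holds as an internal contradiction with a limited consequence. Section 5.1 makes unexpectedness a condition of being an SAE, while 5.3.2 works only if SAEs can be expected. On a literal reading, a serious event judged expected escapes the 24-hour form and the Sponsor notification and is handled at most as an ordinary AE.

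The size cannot be calculated, because no event rates are given. It is probably small in 250 women under observation, and no planned result would change. The conclusion assumes that 5.1 is read as written and that at least one assessor treats some serious event as expected. If all assessors applied the 5.3.2 test and no list existed, nothing would be excluded in practice. The correction is still worth making, because the affected steps are those meant to bring serious events promptly to the Chief Investigator and the Sponsor.

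**What to change.** In the SAE definition in 5.1, delete the words *and unexpected*, so that any untoward occurrence with one of the listed outcomes is an SAE. Leave expectedness only in 5.3.2, as the Chief Investigator's test for JCRO reporting. Sections 5.1 to 5.3.2 then agree. No new exemption is needed, since 5.3.2 already exempts elective admissions for existing conditions.

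The cost is one deletion and possibly a few more SAE forms and Sponsor notices. It needs no extra patients, visits or procedures and no change to the analysis.

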5.3 REPORTING PROCEDURES

All adverse events should be reported. Depending on the nature of the event the reporting procedures below should be followed. Any questions concerning adverse event reporting should be directed to the Chief Investigator in the first instance.

5.3.1 Non serious AEs

All such events, whether expected or not, should be recorded.

5.3.2 Serious AEs

An SAE form should be completed and faxed to the Chief Investigator within 24 hours. However, relapse and death due to endometrial cancer and hospitalisations for elective treatment of a pre-existing condition do not need reporting as SAEs.

All SAEs should be reported to the JCRO at Imperial where in the opinion of the Chief Investigator, the event was:

- 'related', ie resulted from the administration of any of the research procedures; and
- 'unexpected', ie an event that is not listed in the protocol as an expected occurrence

Reports of related and unexpected SAEs should be submitted within 15 days of the Chief Investigator becoming aware of the event, using the NRES SAE form for non-IMP studies. The Chief Investigator must also notify the Sponsor of all SAEs.

Local investigators should report any SAEs as required by their Local Research Ethics Committee, Sponsor and/or Research & Development Office.

6. ASSESSMENT AND FOLLOW-UP

Following the survey/biopsy will continue with routine standard of care and follow up.

End of trial will be defined as when the last patient for recruitment received her operative surgery (and final histology was obtained) and has been followed up for 5 years.

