AIMS (1) Determine the anxiety levels of women with suspected endometrial cancer
(2) Determine factors affecting anxiety levels

OUTCOME MEASURES Primary outcome measures:
(1) Anxiety levels of women with suspected cancer

Secondary outcome measures:
(1) Factors affecting anxiety level

POPULATION 250 women referred to rapid access clinic with postmenopausal bleeding or intermenstrual bleeding.

ELIGIBILITY All women presenting to rapid access gynaecology clinic with postmenopausal bleeding or intermenstrual bleeding

EXCLUSION Anyone lacking capacity. <18years old. Pregnant. Any contra-indication carry out a biopsy

DURATION 1 year

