3. STUDY DESIGN

Paired observational study

Setting: Imperial College NHS Trust Hospitals, London

Participants: 250 women referred to rapid access clinic with postmenopausal bleeding or intermenstrual bleeding.

Duration: 1 year

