3.1 MAIN STUDY

250 consecutive women presenting to the rapid access clinic with postmenopausal bleeding (PMB) and intermenstrual bleeding (IMB) will be approached for consent for inclusion into this study.

Women were given a short 5-minute questionnaire to fill during their first clinic attendance, before seeing any clinician or healthcare provider (see appendix for copy of questionnaire).

The questionnaire had 19 questions, split into 4 broad groups: questions quantifying anxiety/stress levels, factors that might affect anxiety levels, patient's perception of cancer diagnosis and the importance of a quick diagnosis. Patients were asked to score how they perceived their stress levels using a Likert scale. A score of 4 or above was defined as high stress in this study and 3 and below as low stress. Patients were also asked to fill a Generalised Anxiety Disorder 7 (GAD 7) form.

Women were excluded if, in the absence of a translator, they did not have sufficient comprehension of English to fill the questionnaire. Patients were also excluded from the analysis if they omitted 3 or more answers from the questionnaire.

For women needing a pipelle biopsy for clinical indications, the time taken to perform the biopsy, from insertion of the speculum to its removal was recorded in minutes, rounded to the nearest 30 seconds. Women were asked to rank their pain using a visual analogue score (0 to 10, where 0 is no pain and 10 is the worst pain in their life). Women were asked if they would have this procedure again, if they would recommend it to family or friends should they were need it. If women persisted with the procedure, they were asked their motivations for doing so, and what coping mechanisms they used. This paired data was matched to the patient's questionnaire responses.

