4.2 INCLUSION CRITERIA

All women presenting to rapid access gynaecology clinic with postmenopausal bleeding or intermenstrual bleeding

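### Does a 1-year duration beside an end-of-trial rule with 5 years of follow-up call for a change to the plan?

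*Combined protocol and SAP*

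**What the plan says.** The synopsis gives "DURATION 1 year" and section 3 repeats "Duration: 1 year". Neither says whether this is the recruitment period or the whole study.

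Section 6 has two parts. After the questionnaire or biopsy, women return to ordinary care: "Following the survey/biopsy will continue with routine standard of care and follow up". It then sets the closing rule: "End of trial will be defined as when the last patient for recruitment received her operative surgery", her final histology is available, and she "has been followed up for 5 years". No other section says when the study ends.

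Entry depends on symptoms alone. Section 4.2 admits "All women presenting to rapid access gynaecology clinic with postmenopausal bleeding or intermenstrual bleeding", and section 3.1 plans to approach "250 consecutive women presenting to the rapid access clinic". Biopsy data are collected only in a subset: "For women needing a pipelle biopsy for clinical indications". No section makes surgery or a cancer diagnosis a condition of entry or a study procedure.

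**The concern.** Three things look wrong.

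- **Length.** A one-year study cannot contain five years of follow-up. Either the two statements conflict, or the year means recruitment and the total is missing.
- **Trigger.** Closure depends on the last recruit's operation, but women enter because of bleeding and may never need one. Taken literally, the end of the study might then never arrive.
- **Purpose.** Five years are called for, with no follow-up visit, variable, endpoint or analysis attached.

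At stake would be when the study formally closes and what hangs on that date. Section 7 counts a minimum 10-year storage period from completion. Section 5.3 asks for adverse events to be recorded without saying for how long. If the five years were meant to yield outcome data, a whole component of the study would lack an analysis plan.

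**Working it through.** **Step 1: the calendar.** Inputs: a one-year duration (synopsis, section 3) and five years of follow-up for the last patient (section 6). Let r be the time of the last recruitment in years, with 0 ≤ r ≤ 1, and s ≥ 0 the delay to her surgery and histology. The document does not say whether the five years run from recruitment or from surgery.

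- Counted from recruitment, the end of trial is no earlier than r + 5.
- Counted from surgery, it is r + s + 5.

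*If the year is the total duration*, the overrun is at least r + 5 − 1 = r + 4 years. That is 4 years at the extreme r = 0, s = 0, and 5 years if recruitment fills the year (r = 1, s = 0). Any surgical delay adds to it when follow-up runs from surgery.

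*If the year is recruitment*, the total is 1 + 5 = 6 years or more. Nothing conflicts; the sum is simply not written down.

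On the first reading the rule cannot be satisfied at all, since its minimum of 5 years exceeds 1. The second is the only one under which all the statements hold. Section 3 places the duration directly after the number of participants, which fits that reading without proving it.

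**Step 2: the surgery trigger.** Taken literally, closure is undefined if the last woman recruited has no operation. If the last patient means the last among those who have surgery, the rule can be met. The document gives no surgery rate, so the chance of the literal problem cannot be computed.

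**Step 3: what the closing date can affect.** The data items and their timing, from section 3.1, are:

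| Data | When collected |
|---|---|
| 19-question questionnaire, including the Likert stress score | First attendance, before any clinician is seen |
| GAD-7 | Described with the questionnaire; no later time point given |
| Biopsy duration, pain score (0 to 10), acceptability, motivation, coping | Linked to the biopsy, in women who need one; no later time point given |

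The synopsis names anxiety levels as the primary outcome and factors affecting them as the secondary. Section 7 plans medians, quartiles, box plots and Mann-Whitney-Wilcoxon tests of each factor against GAD-7. None of these uses a value recorded after the first attendance or biopsy, and none uses follow-up time. The analysis set is reduced only by insufficient English without a translator or by three or more unanswered items, both settled when the questionnaire is completed. The data entering each test are therefore the same whether the study closes at year 1 or year 6.

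**Step 4: storage.** If completion means the section 6 end point, the minimum storage period ends at about year 6 + 10 = 16 from first recruitment, against 1 + 10 = 11 if the study closes at one year. The period is a minimum in either case, and nothing in the document makes the longer one harmful.

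**The case for a change.** The strongest case for acting is that section 6 is the only closing rule, so it governs even if it came from another protocol. Calling the year recruitment is an inference. On that inference the total is still unstated, and five years of follow-up still have no stated use. The remedy would also be cheap: a few words of text, with no effect on the data.

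Much of this stands as description. The duration is unlabelled, the surgical trigger fits the eligible population poorly, and no follow-up endpoint or analysis exists.

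The consequences do not stand up as well. The lack of a visit schedule is partly answered by section 6 itself, which leaves women in routine care. Nor is the period necessarily empty: section 6 refers to surgery and histology, and section 4.4 keeps clinical details on file up to withdrawal.

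Adverse-event recording is the one duty that might lengthen. Because section 5.3 gives no time window, the added work could be nil if recording stops at the visit, and any larger figure would rest on an invented window. Section 5.3.2 also exempts relapse and death from endometrial cancer, and elective admissions for pre-existing conditions, from serious-event reporting. It limits onward reports to the research office to related and unexpected events. Non-serious events are still recorded, and the sponsor is still told of serious ones, so the duty is reduced but not removed.

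That a correction is cheap does not give it a benefit. Sections 3.1 and 7 describe questionnaire collection and analysis largely in the past tense, which leaves an amendment even less to achieve.

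**Conclusion.** The inconsistency is genuine but administrative, and no change to the plan is called for. Its size is an overrun of at least 4 years, or about 5 or more if recruitment fills the year, on the total-duration reading. On the recruitment reading it is an unstated total of about 6 years or more. Its effect on the anxiety results is nil: no outcome, test, estimate, precision or source of bias depends on the closing date, and no patient-safety risk has been shown.

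This rests on two assumptions. The first is that the GAD-7 and the biopsy items are collected at the visits to which section 3.1 attaches them. The second is that no five-year outcome is to be analysed, which agrees with the stated aims, outcomes and analysis. A long-term outcome would be a new objective needing its own plan, and nothing in the document indicates one. An analyst can read the year as recruitment and carry out section 7 as it stands.

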7. STATISTICS AND DATA ANALYSIS

Microsoft excel was used to provide the graphs and pie charts for demographics. SPSS version 25 was used to perform all the sub analyses. Median, quartile ranges, box and whiskers plots were created for each variable. A Mann-Whitney-Wilcoxon test was used to assess for association between each factor and anxiety as measured with GAD 7 score.

Data and all appropriate documentation will be stored for a minimum of 10 years after the completion of the study, including the follow-up period.

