2. STUDY OBJECTIVES

Objectives:

- (1) Determine the anxiety levels of women with suspected endometrial cancer
- (2) Determine factors affecting anxiety levels

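### The second objective is to find factors affecting anxiety, but section 7 plans only separate unadjusted tests, with no joint model and no estimate with a confidence interval

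*Combined protocol and SAP*

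**What the plan says.** Section 2 gives two objectives, and the second is to "Determine factors affecting anxiety levels". The summary lists "Factors affecting anxiety level" as the only secondary outcome. Section 3 calls the design a "Paired observational study", so no factor is assigned by the study.

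Section 3.1 describes the data source: "Women were given a short 5-minute questionnaire to fill during their first clinic attendance". The 19 items fall into four groups, which include "questions quantifying anxiety/stress levels, factors that might affect anxiety levels" and the patient's "perception of cancer diagnosis and the importance of a quick diagnosis". On missing answers it says: "Patients were also excluded from the analysis if they omitted 3 or more answers from the questionnaire". Women with one or two blanks therefore stay in.

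Section 7 is the whole analysis plan. It names graphs for demographics and, for each variable, medians, quartiles and box plots. Its only inferential step is: "A Mann-Whitney-Wilcoxon test was used to assess for association between each factor and anxiety as measured with GAD 7 score".

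**The concern.** The objective asks what affects anxiety, while section 7 can show only which items are associated with GAD-7 one at a time. Because the same women answer every item at one visit, correlated items are plausible. A one-factor test cannot separate a factor from a proxy for another item, or from a background variable. Followed as written, the plan could report a proxy as a factor affecting anxiety.

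A separate gap is that a p-value gives neither the size of a difference nor its uncertainty. The planned medians and quartiles describe groups but put no interval around a difference. A reader could not tell a small effect, precisely estimated, from a result too imprecise to interpret.

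**Working it through.** **What the documents supply.** They give 250 women, one unadjusted test per factor, and GAD-7 as the outcome. They give no alpha, effect size, group split or correlation, and the questionnaire appendix is not in the available text. There is no figure in the plan to reproduce, and everything below is illustration on assumed inputs.

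**Step 1: a two-factor check.** Factor A is split 50/50 and has no effect. Factor B shifts anxiety by *e* SD, and its prevalence differs between the A groups by *d*. The expected spurious difference for A is *d × e*. With *e* = 0.5 this is 0.2 × 0.5 = 0.10 SD, 0.4 × 0.5 = 0.20 SD and 0.6 × 0.5 = 0.30 SD (simulated: 0.10, 0.19, 0.30). At n = 250 and a 0.05 level, the Mann-Whitney test of A rejects in about 12%, 31% and 62% of studies. Over *e* = 0.3 to 0.8 and the same values of *d*, it rejects in 8% to 95%. A linear model adjusted for B rejects in 4% to 5%.

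**Step 2: a setting closer to this questionnaire.** There were 2,000 replicates per cell with n = 250, and a skewed 0–21 score with assumed quartiles 2, 4 and 8. There are 5 or 10 candidate factors with common latent correlation *r*. One of them drives anxiety (latent correlation *q*), and the tested factor is split 50/50 with no direct effect. The other factors are recorded on five ordered levels. A background variable correlates 0.2 with every factor and with anxiety. The table shows how often the tested factor is flagged at 0.05; the adjusted analyses are proportional odds models.

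| r | q | Mann-Whitney (5- / 10-factor run) | Background only | Joint, 5 factors | Joint, 10 factors |
|---|---|---|---|---|---|
| 0.3 | 0.1 | 9.9% / 9.7% | 5.6% | 5.3% | 5.3% |
| 0.3 | 0.2 | 16.6% / 16.7% | 8.1% | 5.1% | 6.0% |
| 0.3 | 0.3 | 26.8% / 27.2% | 14.8% | 5.1% | 6.4% |
| 0.5 | 0.1 | 14.9% / 13.6% | 7.5% | 6.4% | 5.2% |
| 0.5 | 0.2 | 29.8% / 30.2% | 16.5% | 5.3% | 5.2% |
| 0.5 | 0.3 | 51.3% / 52.6% | 36.2% | 5.3% | 4.6% |

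Adjusting for background alone is not enough; the other factors have to be in the model. If the other items are split in two rather than kept on five levels, the joint model flags 5.1% to 6.9% (5 factors, *q* = 0.1 and 0.3). Without the background variable, the Mann-Whitney range is 6% to 46%.

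**Step 3: what an interval would show.** In the same setting the mean standard error of the unadjusted log odds ratio is 0.222. The 95% limits are the estimate divided and multiplied by exp(1.96 × 0.222) ≈ 1.545. An estimate of 1.0 would be compatible with about 0.65 to 1.545. On a mean-difference scale the half-width is 1.96 × √(1/n₁ + 1/n₂). That is 1.96 × √(1/125 + 1/125) = 0.25 SD for a 50:50 split and 1.96 × √(1/25 + 1/225) = 0.41 SD for 10:90.

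**Step 4: price of adjustment.** The joint model's standard error is 0.239 to 0.271, and 0.239/0.222 = 1.08 and 0.271/0.222 = 1.22. A factor with 80% power unadjusted then has power Φ((1.96 + 0.84)/1.08 − 1.96) ≈ 0.74 down to Φ((1.96 + 0.84)/1.22 − 1.96) ≈ 0.63. Ten factors and two background terms leave 250/12 ≈ 21 women per coefficient.

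**Step 5: missing answers.** Assume independent blanks on 19 items, with women who have 0 to 2 blanks retained. The share of retained women lost to a complete-case model with *m* items is 1 − P(no blank in *m* items and at most 2 in the other 19 − *m*) / P(at most 2 in 19). At blank rates of 1% and 3% this is 1.0% and 2.7% for one item, 4.9% and 13.2% for five, and 9.5% and 25.0% for ten.

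**The case against.** The strongest reply is that section 7 claims only association. In the simulations the tested factor really is associated with anxiety, through its correlates, so flagging it is not a false positive of the planned test. It becomes an error only when reported as an effect, and association wording alone would cure that. This stands as a reading of the 10% to 53%: it measures how often a proxy would be picked up, not a type I error rate. It does not settle the matter, because the summary and section 2 still promise factors that affect anxiety, and an association also needs an estimate and an interval.

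Second, the simulations treat the correlated driver as a confounder. If the tested factor acts through the driver, the unadjusted result is right and the joint model hides a real effect. This also stands, and it is why the choice of items in the model must be argued.

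Third, part of the excess comes from the assumed background variable, especially at the low end, and the number and content of the factor items cannot be seen. The size is therefore uncertain, but the absence of the analysis is not.

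Finally, this is a secondary outcome, and the past tense in sections 3.1 and 7 suggests that data may be in hand. Both limit the severity; neither removes the gap.

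**Conclusion.** The concern holds. Nothing in the plan takes the factors together or puts an interval around a difference, so the second objective cannot be answered as worded. On the assumed inputs, a factor with no direct effect is flagged in 10% to 53% of studies by the planned test and in 5% to 6% by a joint model. Without the assumed background variable the planned test flags 6% to 46%. These figures depend on the assumed correlations, the 0.05 level and the driver being a confounder rather than a mediator. Adjustment helps only for confounders that were measured. The primary aim, describing anxiety levels, is unaffected. This should be corrected, but it does not invalidate the study.

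**What to change.** In section 7:

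1. Keep the Mann-Whitney tests as unadjusted description.
2. Add a regression of GAD-7, for example proportional odds, with the candidate factors entered together. Include recorded background variables such as presenting symptom (PMB or IMB) and, if recorded, age. These two overlap, so keep one if the model cannot separate them.
3. Leave out of a factor's model any item that may lie on its pathway. For example, enter the perception-of-cancer items only in a second model and read only their own estimates from it. Do not adjust for the anxiety/stress items, which measure the outcome itself.
4. For every factor tested, report the unadjusted and adjusted estimates side by side with 95% confidence intervals.
5. Label the factor analysis exploratory and word conclusions as associations.
6. Preferably use multiple imputation for the one or two blanks that section 3.1 tolerates.
7. If the data are already collected, state that the adjusted analysis was added afterwards.

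The core is items 2 to 5. The cost is about a paragraph of text and a modest amount of analysis, with no new data. Standard errors rise by about 8% to 22% on the assumed correlations. Without imputation, a joint model of 5 to 10 items could lose about 5% to 25% of retained women at blank rates of 1% to 3%.
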